### 7.3. Safety Population

The Safety Population will include all subjects who receive any amount of investigational product within the DB phase. Treatment assignment will be based on the actual treatment received.

### 7.4. Efficacy Evaluable (EE) Population

All subjects who complete the DB phase according to the indicated doses of investigational product and atorvastatin without any major protocol deviations that potentially affect the efficacy of the study drug will be included in the EE Population, which is the primary population used for efficacy analyses. If greater than 20% of the ITT Population subjects have such deviations as determined prior to database lock of the DB (see [Section 8.2](#)), then all efficacy analyses and selected other summaries will be repeated using the ITT Population.

### 7.5. OCA Pharmacokinetic (PK) Population

The PK Population will include all OCA treated subjects who consent to participate in the PK assessments and have at least one confirmed fasted OCA concentration. Subjects must have been fasting for at least 8 hours prior to dosing and must not have any major protocol deviations that potentially affect exposure levels.

## 8. STUDY POPULATION

### 8.1. Subject Disposition

Subject disposition information will be summarized and listed for all subjects. Summaries will include the following: the number of subjects randomized, the number of subjects in each analysis population, the number of subjects at each study site, the number of subjects completing the DB phase (Week 16) and each scheduled visit (Week 2, 4, 8, and 12), the primary reason for discontinuation from the DB phase, and the number of subjects enrolling in the LTSE. A subject will be considered as completing the DB phase if the subject has non-missing assessment of LDL metabolism at all scheduled visits (Weeks 2, 3, 4, 12, and 16). Percentages will be based on the ITT Population.

The reasons for discontinuation of investigational product (OCA/PBO) and discontinuation of study atorvastatin will be summarized in a similar manner.

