## **4. STUDY DESIGN AND PLAN**

This is a Phase 2, double-blind, randomized, placebo-controlled, multicenter study, evaluating the effects of OCA, and the subsequent addition of statin therapy, on lipoprotein metabolism in subjects with NASH with fibrosis stage 1 to 4, but no evidence of hepatic decompensation, in the DB phase, followed by an open-label LTSE phase to evaluate long term safety and efficacy.

Approximately 80 subjects with histological evidence of definite or probable NASH, who meet all inclusion and none of the exclusion criteria will be enrolled in the study. The histological evidence of definite or probable NASH will be based on the central read of a liver biopsy obtained no more than 1 year prior to randomization and a nonalcoholic fatty liver disease activity score (NAS) of 4 or greater. Subjects not using statin therapy (ie, statin-free) and statin-treated subjects may be enrolled. Statin-treated subjects will be required to stop statin treatment (after signing informed consent) for up to 5 weeks, including a 4-week statin washout period, prior to Randomization/Day 1.

Subjects will have a screening period of up to 5 weeks prior to Randomization/Day 1. At the Randomization (Day 1) Visit, subjects will be randomized in a 1:1:1:1 ratio to receive OCA 5 mg, OCA 10 mg, OCA 25 mg, or placebo, orally, once daily, for 16 weeks. Randomization will be stratified by the pre-randomization fasting serum LDLc ( $\leq$ 125 mg/dL or  $>$ 125 mg/dL) and baseline fibrosis stage (stage 1, 2 or stage 3, 4).

[figure not shown]
Subjects will attend on-site clinic visits at Weeks 2, 4, 8, 12, and 16 and will be contacted at Weeks 6, 10 and 14 to assess safety and treatment compliance. At the Week 4 Visit, all subjects will initiate treatment with atorvastatin at a dose of 10 mg once daily. At the Week 8 Visit, atorvastatin will be increased to 20 mg once daily (if 10 mg daily is tolerated), and continued for an additional 4 weeks. After 4 weeks of treatment at 20 mg, the atorvastatin dose may be titrated (up or down) as clinically indicated. The final visit during the DB phase will occur at Week 16, after which subjects may continue into the open-label LTSE.

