## **8.2. Protocol Deviations**

Protocol deviations for missed visits, missed assessments, out of window visits or assessments, and violations of inclusion/exclusion criteria will be determined based on available data. The clinical research associates will collect all other protocol deviations. Major protocol deviations identified during the DB phase that could potentially affect the conclusions of the study or result in a subject's removal from an analysis population will be classified as such prior to database lock of the DB phase. Major protocol deviations will be summarized by deviation category and treatment group. All protocol deviations and their classifications will be presented in a listing. Subjects with protocol deviations that result in a subject's removal from the ITT, Safety, EE, or PK Populations will be flagged in a listing.

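### The SAP's definition of completing the double-blind phase lists the wrong weeks and demands every visit, and Section 9's condition on ITT analyses contradicts Section 9.1 and Appendix A

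*SAP*

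**What the plan says.** **Completion.** Section 8.1 treats a subject as completing the DB phase if the subject has "non-missing assessment of LDL metabolism at all scheduled visits (Weeks 2, 3, 4, 12, and 16"). The sentence before it asks for counts of subjects "completing the DB phase (Week 16) and each scheduled visit (Week 2, 4, 8, and 12"), and the same summary reports "the primary reason for discontinuation from the DB phase". Section 4 states: "Subjects will attend on-site clinic visits at Weeks 2, 4, 8, 12, and 16".

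**Population.** Section 7.4 builds EE from subjects who complete the DB phase on the indicated doses and have no major deviation that could affect efficacy. It calls EE the set "which is the primary population used for efficacy analyses". It cross-refers to Section 8.2 and not to Section 8.1.

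**When ITT is analysed.** There are four statements:
- Section 7.4 repeats all efficacy analyses in ITT under this condition: "If greater than 20% of the ITT Population subjects have such deviations as determined prior to database lock of the DB".
- Section 9 allows ITT analyses only if more than 20% of ITT subjects are excluded from EE.
- Section 9.1 commits, with no condition, to an ITT sensitivity analysis of the primary endpoints under both the by-visit and the repeated-measures ANCOVA.
- Appendix A lists ITT tables for LDL, HDL and VLDL with no condition attached.

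**Deviations.** Section 8.2 derives from the data "Protocol deviations for missed visits, missed assessments, out of window visits or assessments". Major deviations leading to a subject's "removal from an analysis population will be classified as such prior to database lock of the DB phase".

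**The concern.** The SAP has no other definition of DB completion, and this one cannot be programmed as written. Correcting the weeks leaves a second problem: requiring every visit turns a missed intermediate sample into non-completion, so completers and discontinued subjects no longer account for everyone in the disposition table.

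The ITT instructions cannot all be followed. If 20% or fewer of ITT subjects are outside EE, Section 9 forbids analyses that Section 9.1 requires and Appendix A lists.

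EE is selected after randomisation on completion, dosing and deviations. In a study that Section 6.2.8 calls descriptive, the estimates are the product. The reader therefore needs to know which subjects they come from and whether an ITT estimate will stand beside them.

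**Working it through.** **1. Visit lists side by side**

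| Source | Weeks |
|---|---|
| Section 4, clinic visits | 2, 4, 8, 12, 16 |
| Section 8.1, disposition counts | 2, 4, 8, 12, and 16 as the end of the DB phase |
| Section 8.1, completion rule | 2, 3, 4, 12, 16 |

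Week 3 appears in neither of the first two lists, and Week 8 is missing from the third. No subject can have a scheduled Week 3 value, so the literal number of completers is 0.

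**2. The rule with the weeks corrected.** Take a subject with values at Weeks 2, 4, 12 and 16 and none at Week 8. Four of five visits are present, so the subject fails the rule. The subject stayed to the end, so there is no reason for discontinuation to report. The subject belongs to neither group in the summary.

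**3. From completion to EE.** Section 7.4 requires completion of the DB phase. Section 8.1 is the only place that says what this means, but Section 7.4 does not cite it. The link is an inference from shared wording. If it holds, the subject in step 2 is also outside EE despite having the Week 16 value that the primary endpoint needs.

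**4. The 20% condition in numbers.** Section 4 plans about 80 subjects. Assume all are dosed, so that ITT = 80.
- 16/80 = 20.0%, which does not exceed 20%.
- 17/80 = 21.25%, which does.

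Under Section 9, up to 16 subjects can be outside EE with no ITT analysis allowed. Section 9.1 requires the ITT analysis of LDL at any count from 0 upwards. Reading Section 9.1 as an exception to Section 9 does not settle the matter, because the HDL and VLDL tables planned in ITT are secondary and lie outside Section 9.1.

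**5. The two triggers.** Let *d* subjects have major deviations, let *s* others stop early, and let *k* of those *s* be classed as major deviations under Section 8.2.
- Section 9 counts (*d* + *s*)/80.
- Section 7.4 counts (*d* + *k*)/80.

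The counts are equal when *k* = *s*. As an illustration with assumed values *d* = 10 and *s* = 10, Section 9 gives 20/80 = 25%. Section 7.4 exceeds 20% only if 10 + *k* > 16, that is *k* ≥ 7. Whether the triggers differ therefore depends on how early stoppers are classified.

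**6. Secondary lipid parameters against Appendix A.** Section 3.2.1 lists 3 HDL + 3 VLDL + triglycerides + total cholesterol + 5 apolipoproteins + Lp(a) + PCSK9 = 15. Section 3.2.2 lists 4. The total is 19.

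| Tabling | Parameters | Count |
|---|---|---|
| EE only | total cholesterol and triglycerides (14.2.4.1, 14.2.4.2): 2; apolipoproteins and Lp(a) (14.2.5): 6; reverse cholesterol (14.2.6): 4 | 12 |
| EE plus repeated-measures tables | 3 HDL, 3 VLDL | 6 |
| In no table title | PCSK9 | 1 |

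12 + 6 + 1 = 19, and 12/19 = 63%. The population cell of Table 14.2.3.2.3 (VLDL size and particle concentration) is blank and is counted here as ITT, like its neighbours. If it is not ITT, the EE-only count is 14.

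**The case against.** The week list is plainly a slip, since the sentence before it gives the right visits and any programmer would query it. That is fair, but correcting the weeks does not remove the every-visit requirement.

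Appendix A also shows the intent on ITT. It marks Table 14.1.4.3 as produced only above 20% and puts no such mark on the ITT lipid tables. Sections 7.4 and 9.1 can stand together. This stands too, and it narrows the direct conflict to the word *only* in Section 9.

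On the triggers, Section 8.2 already records missed visits and assessments as deviations and provides for classifying as major those that remove a subject from a population. An early stopper would probably be counted under both rules, which largely closes the gap.

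A reader might infer that the 12 EE-only parameters are an error because Section 9.2 says that secondary parameters are analysed like the primary ones. The SAP does not support that. Section 9 bases secondary analyses on EE, Section 9.1 confines its ITT commitment to the primary analysis, and Section 9.2 goes on to describe summaries and least squares estimates, not populations. Tabling them in EE follows the plan.

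Finally, ITT adds less than it may seem. Analyses use observed data, so a subject with no Week 16 value contributes nothing to the Week 16 ANCOVA. Only the repeated-measures model uses that subject's earlier visits.

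**Conclusion.** Two things are wrong as written. The completion definition names a Week 3 visit that does not exist, omits Week 8 and, once corrected, still makes non-completers of subjects who reach Week 16. Section 9's restriction on ITT analyses contradicts Section 9.1 and the ITT tables in Appendix A.

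Two further points are weaker. That Section 8.1 governs EE membership is an inference. That the triggers in Sections 7.4 and 9 diverge is possible but depends on classification under Section 8.2.

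A reader might go on to infer that the EE results are biased, or that a particular number of subjects will be lost. The SAP gives no missing-data rate, so neither the number nor the size or direction of any bias can be derived. Nor does the Section 7.4 wording leave exclusions without limit: Section 8.2 brings missed visits into the deviation count, and Section 9 has its own trigger on exclusions.

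The firm figures are the threshold (up to 16 of 80 outside EE before Section 9 allows ITT, assuming all 80 are dosed) and the table count (12 of 19, taking the blank population cell as ITT). For LDL, the planned ITT tables already cover most of the selection concern.

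**What to change.** **To correct:**
- In Section 8.1, change the weeks to 2, 4, 8, 12 and 16 where the visits are listed, and define DB completion by the Week 16 assessment instead of every visit.
- In Section 7.4, state which completion definition EE uses.
- In Sections 7.4 and 9, remove the 20% condition so that ITT analyses are unconditional, as in Section 9.1. The difference between the two triggers then no longer matters.

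**Inexpensive improvement, not a correction of an error:**
- Add ITT versions of Tables 14.2.4.1, 14.2.4.2, 14.2.5 and 14.2.6 with the models in Sections 6.2.3 and 6.2.4. The repeated-measures model matters most, for the reason given above.
- Include PCSK9 in a table, and fill the blank population cell of Table 14.2.3.2.3.

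EE may remain the primary population, and the primary model need not change. The cost is SAP wording and four added ITT tables. The data, the ITT population and both models already exist, and the only drawback is a slightly longer set of outputs.

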## **8.2. Protocol Deviations**

Protocol deviations for missed visits, missed assessments, out of window visits or assessments, and violations of inclusion/exclusion criteria will be determined based on available data. The clinical research associates will collect all other protocol deviations. Major protocol deviations identified during the DB phase that could potentially affect the conclusions of the study or result in a subject's removal from an analysis population will be classified as such prior to database lock of the DB phase. Major protocol deviations will be summarized by deviation category and treatment group. All protocol deviations and their classifications will be presented in a listing. Subjects with protocol deviations that result in a subject's removal from the ITT, Safety, EE, or PK Populations will be flagged in a listing.

## **8.3. Demographic and Baseline Characteristics**

Demographic variables will include the following:

- Age at informed consent
- Age at informed consent categorized as < 65 years and  $\geq$  65 years
- Sex
- Race/ethnicity

Other Baseline characteristics will include the following:

- Weight (kg)
- Height (cm) at Screening visit
- BMI ( $\text{kg}/\text{m}^2$ )
- BMI categorized as < 30  $\text{kg}/\text{m}^2$  and  $\geq$  30  $\text{kg}/\text{m}^2$
- Liver fibrosis stage using NASH Clinical Research Network (CRN) scoring criteria categorized as Stage 1a, 1b, 1c, 2, 3, 4
- Liver fibrosis stage using NASH CRN scoring criteria categorized as Stage 1, 2 and Stage 3, 4
- Liver fibrosis stage using modified Ishak scoring criteria categorized as Stage 1, 2, 3, 4, 5, 6
- NAFLD Activity Score (NAS) and its components categorized as:
  - Steatosis: 0, 1, 2, 3
  - Hepatocellular Ballooning: 0, 1, 2
  - Lobular Inflammation: 0, 1, 2, 3
- NAS categorized as < 6 and  $\geq$  6 total points
- Diabetes status: Yes, No (defined as subjects with any condition in the Endocrine/Metabolic body system and medical term containing “diabetes type II” or

similar derivative, as collected on the eCRF Medical History; if unable to determine what type of diabetes, set diabetes status to yes)

- Concomitant medication use (ongoing on Day 1. If it cannot be determined whether the medication was ongoing at the Day 1 visit due to a partial start or stop date, then it will be counted as ongoing.)
  - Vitamin E (ATC codes = 'A11HA' and Trade name = 'E VITAMIN')
  - TZD (ATC codes starting with 'A10BG')
  - Antidiabetic medication (ATC codes starting with 'A10')
  - Antihypertension medication (ATC codes starting with 'C02')
- Screening fasted serum LDL cholesterol concentration categorized as  $\leq$  and  $> 125$  mg/dL
- Screening HDL cholesterol concentration (mg/dL) categorized as  $\geq$  lower limit of normal (LLN),  $<$  LLN
- Baseline liver function test results as a continuous variable and categorized as follows by the LLN and the upper limit of normal (ULN) unless otherwise specified:
  - ALT:  $\leq 40$  U/L,  $> 40$  U/L and  $\leq$  ULN,  $>$  ULN
  - AST:  $\leq 40$  U/L,  $> 40$  U/L and  $\leq$  ULN,  $>$  ULN
  - Direct Bilirubin:  $\leq$  ULN,  $>$  ULN
  - Total Bilirubin:  $\leq$  ULN,  $>$  ULN
  - Platelets:  $\geq$  LLN,  $<$  LLN

Arithmetic summary statistics as described in [Section 6.2.1](#) will be presented for age, weight, height, BMI, and key liver function tests. Frequency counts and percentages will be presented for age groups, sex, race/ethnicity, BMI categories, liver fibrosis stage categories, NAS, concomitant medication use, diabetes status, LDL and HDL cholesterol categories, and key liver function test categories. Race and ethnicity will be summarized as follows:

- Race
  - American Indian or Alaska Native
  - Asian
  - Black or African American
  - Native Hawaiian or Other Pacific Islander
  - White
- Ethnicity
  - Hispanic or Latino
  - Not Hispanic or Latino

- Not reported
- Unknown

Demographic and Baseline characteristics will be summarized for the ITT, Safety, PK, and EE Populations (if warranted). All demographic and Baseline characteristics will be presented in data listings.

#### **8.4. NASH Disease History**

Baseline NASH disease characteristics will be summarized using data collected from the Medical History eCRF. Assessments include the following:

- Age at NASH diagnosis
- Age at NASH diagnosis categorized as  $< 50$  years and  $\geq 50$  years
- Duration of NASH in years at time of informed consent
- Duration of NASH categorized as  $\leq$  median years and  $>$  median years
- Method of confirmation for NASH diagnosis categorized as liver biopsy, elevated liver enzymes, non-invasive imaging, or other.

Arithmetic summary statistics as described in [Section 6.2.1](#) will be presented for the age at NASH diagnosis and the duration of NASH. All other categorical NASH disease characteristics will be summarized using frequency counts and percentages. NASH disease history will be summarized for the ITT Population and, if warranted, the EE Population. NASH disease history will be presented in a data listing.

#### **8.5. Alcohol Use Disorders Identification Test (AUDIT)**

Baseline, Day 1, Week 16, and Early Termination/End of Study AUDIT scores will be summarized using arithmetic summary statistics as described in Section 6.2.1 and presented in a data listing.

#### **8.6. Tobacco Use**

Arithmetic summary statistics as described in Section 6.2.1 will be presented for duration of use (among former and current users) and amount of daily cigarette, cigar, smokeless tobacco (amount of pinches), pipe (amount of pipefuls), and other tobacco use (among former and current users) at Screening. Frequency counts and percentages will be presented for tobacco use (Yes/No) and frequency of use for each type of tobacco (among former and current users). Tobacco use data will be presented in a data listing.

#### **8.7. Statin History**

Baseline statin history use characteristics will be summarized using data collected from the Statin History Use eCRF. Assessments include the following:

- Statin use (Yes/No)
- Name of statin used

- Last statin medication dose
- Duration of statin use (years)
- Primary reason statin stopped

All categorical statin history will be summarized using frequency counts and percentages. Overall statin use will be summarized using the ITT Population as the denominator. The other characteristics will be summarized for each statin used with the number of subjects using the corresponding statin as the denominator. The continuous characteristics for each statin will be summarized using arithmetic summary statistics as described in [Section 6.2.1](#). Subjects may have used more than 1 statin. All statin use history data will be listed (including comments).

## **8.8. Family Cardiovascular History**

Baseline family cardiovascular history will be summarized using data collected from the Family Cardiovascular History (First Degree) eCRF. Assessments include the following:

- Family history of myocardial infarction, angina or dyslipidemia? (Yes/No)
- Person with event (father, mother, brother, sister, other - specify)
- Myocardial infarction (Yes/No) and age at time of event (categorical)
- Angina (Yes/No) and age at time of event (categorical)
- Dyslipidemia (Yes/No)

All categorical family cardiovascular history will be summarized using frequency counts and percentages for the ITT Population. Subjects may have more than one family member and type of event recorded. All family cardiovascular history data will be listed.

## **8.9. General Medical History**

Verbatim medical history terms on eCRFs will be mapped to preferred terms and system organ classes using the Medical Dictionary for Regulatory Activities (MedDRA; version 18.1). Frequency counts and percentages of the number of subjects reporting an abnormal Baseline medical history will be summarized by MedDRA system organ class and preferred term using the ITT Population.

Summaries that are displayed by system organ class and preferred term will be ordered by descending order of incidence for all OCA treated subjects of system organ class and by preferred term within each system organ class.

Medical History data will be presented in a data listing.

## **8.10. Prior and New Concomitant Medications**

Verbatim terms on eCRFs will be mapped to ATC class and preferred term using the World Health Organization Drug Dictionary Enhanced (WHODDE; WHO-DDE-B2 Dec2015).

Pretreatment medications are those medications with start and stop dates prior to the first dose of investigational product in the DB phase. Prior concomitant medications are those medications started prior to, and continued after, the first OCA dose in the DB phase. New concomitant

medications are those medications that were started after the first OCA dose in the DB phase. If it cannot be determined whether the medication was a new concomitant medication due to a partial start or stop date or if the medication is taken on the same date as the first OCA dose in the DB phase, then it will be counted as a new concomitant medication.

Pretreatment medications will be presented in listings only. Prior and new concomitant medications will be summarized by World Health Organization ATC class and preferred term using the ITT Population. New concomitant medications will be summarized separately. These summaries will present the number and percentage of subjects using each medication. Subjects may have more than 1 medication per ATC class and preferred name. A subject is counted once when 1 or more medications is reported at the ATC class or preferred term level. Each summary table will be ordered by descending order of incidence, for all OCA-treated subjects, of ATC class and preferred term within each ATC class.

Prior and new concomitant medications will be presented in a data listing.

